5.3 Inclusion of Women and Minorities

Both male and female children and adults as well as members of all ethnic groups are eligible for this trial. The proposed study population is illustrated in the table below.

Race and Ethnicity of Children and Adults with Neuroendocrine or other Somatostatin Receptor Positive Tumors Referred to UIHC Specialty Clinics						
Year	2009	2010	2011	2012	2013	2014
Solid Tumors	40	38	61	41	45	Pending
Male	29	20	32	16	21	
Female	11	18	29	25	24	
Hispanic Ethnicity	2	1	3	4	3	
African American	2	2	2	1	6	
American Indian	0	0	0	0	0	
Pacific Islander	0	0	0	0	3	
White	36	35	55	36	33	
Other*		1	1	0	1	

The 2010 US Census reports the following minorities living in Iowa: 3.2% African-American, 0.1% Native Hawaiian/Pacific Islanders, 0.5% American Indian/Alaskan native, 2.0% Asian, and 5.3% Hispanic.

6.0 Imaging and Treatment Plan

**Phase II,
Dosimetry-Guided, Peptide Receptor Radiotherapy (PRRT) with
⁹⁰Y-DOTA-tyr³-Octreotide (⁹⁰Y-DOTATOC) in Children and Adults
with Neuroendocrine and other Somatostatin Receptor Expressing Tumors**

Treatment Cycles and Followup		Imaging and Treatment Schedule	Initial ⁹⁰ Y-DOTATOC Dose	Cumulative ⁹⁰ Y-DOTATOC Dose	Cumulative Renal Radiation
Cycle 1 Week 1	Day 1	Physical exam with height, weight, vitals, labs, list, GFR, pregnancy test; QOL questionnaire Start 18 hrs IV/PO fluids			
	Day 2	⁹⁰ Y-DOTATOC + IV amino acids Continue IV/PO fluids for 48 hrs	50 mCi/m ² in children; 120 mCi in adults	120 mCi maximum	
	Day 4	⁹⁰ Y-DOTATOC PET/CT			
Cycle 2 Week 7-9	Day 1	Physical exam with height, weight, vitals, labs, med list, GFR, pregnancy test Start 18 hrs IV/PO fluids			
	Day 2	⁹⁰ Y-DOTATOC + IV amino acids Continue IV/PO fluids for 48 hrs	Dosimetry determined	270 mCi maximum	
	Day 4	⁹⁰ Y-DOTATOC PET/CT			
Cycle 3 Week 13-17	Day 1	Physical exam with height, weight, vitals, labs, list, GFR, pregnancy test Start 18 hrs IV/PO fluids			
	Days 2-3	⁹⁰ Y-DOTATOC + IV amino acids Continue IV/PO fluids for 48 hrs	Dosimetry determined	420 mCi maximum	≤ 23 Gy
FU	3 months after treatment 3	Physical exam with height, weight, vitals, labs, med list, GFR; QOL questionnaire, diagnostic CT (MRI)			
	6-9 months after treatment 3	Physical exam with height, weight, vitals, labs, med list, GFR; diagnostic CT (MRI) ⁶⁸ Ga-DOTATOC PET/CT;			

Treatment consists of 3 cycles, 6-8 weeks apart. Cycle 1 dose is fixed. Cycles 2 and 3 doses will be determined by dosimetry-based calculation of renal doses from previous cycles; total renal dose ≤ 23Gy.

6.1 Delivery of Therapeutic Infusion

⁹⁰Y-DOTA-tyr³-Octreotide and amino acid infusions will be administered on Day 2 of each treatment cycle. A large IV, either 20 gauge peripheral IV or a PICC line, will be inserted to provide free flow of the hyperosmolar amino acid solution, thus avoiding local inflammation with risk of blistering. Amino acid infusion will begin 30 min prior to infusion of ⁹⁰Y-DOTATOC and continue 3.5 hrs after infusion of radiotherapeutic drug. If rate of amino acid infusion is decreased due to nausea, the length of infusion

may be longer than 3.5 hrs. There will be rescue Sandostatin available (subcutaneous bolus of 200 µgm (200 µgm/mL)) in case of carcinoid crisis after ⁹⁰Y-DOTATOC infusion has been completed.

6.2 Methods for Dosimetry Estimates

Renal dosimetry: Each subject will have renal ⁹⁰Y-DOTATOC time-of-flight (TOF) PET/CT images taken within approximately 48 hours (40-56 hours) after the administration of ⁹⁰Y-DOTATOC.

Bone Marrow dosimetry: Blood dosimetry will be performed as a surrogate of bone marrow dosimetry. Blood samples will be obtained prior to start of Amino Acid infusion, again within 1-4 hours after administration of ⁹⁰Y-DOTATOC and at 48 hrs (40-56 hrs).

6.3 Measurement of Renal Dose

The following information is required to estimate the dose to the kidneys:

- a) An estimate of the radioactivity accumulated in the kidneys,
- b) The kinetics of the radioactivity, and
- c) The size (mass) of the kidneys.

The renal accumulation of the radiopharmaceutical will be measured with Y-90 DOTATOC time-of-flight PET-CT imaging. A standard of Y-90 will be also imaged. PET images will be reconstructed with an OSEM iterative algorithm that incorporates the time of flight information. The kidney mass will be obtained from CT images.

The methods of kinetic analysis of the renal clearance of Y-90 DOTATOC is modified based on our previous experience. Our analysis of 47 prior administrations demonstrate that the renal clearance of Y-90 DOTATOC follows a biexponential pattern with the majority of the radiation exposure to the kidneys coming from the slow (long) component of clearance after the initial fast elimination. The rate constant of the slow component was gaussian distributed with a standard deviation less than 30% of the mean. This allows us to use a population based rate constant for slow clearance adjusted based on the uptake at 48 hours. The estimated renal radiation dose using this approach shows excellent correlation with the measured radiation dose (See *Appendix 1t: Single Timepoint Dose Estimate for Exponential Clearance*) and allows for a clinically feasible personalized treatment dosimetry with one follow-up visit after 48 hours of treatment administration. The information on renal uptake, renal mass and residence time will be entered into OLINDA software to calculate the radiation dose.

The Phase II studies of ⁹⁰Y-DOTA-tyr³-Octreotide administered to adults suggest that the safe range of ≤ 23 Gy for radiation to kidneys delivered by external beam radiation, is more likely 30-35 Gy when delivered as divided doses of targeted internal radiation⁵⁸. Furthermore, there were no dose limiting renal toxicity events in children or young adults enrolled in the Phase I study. Nevertheless, because of the young age of pediatric subjects described in Aim 1, we limited the total dose to kidneys, including any previous external beam radiation to ≤ 23 Gy. The dose to kidneys measured in Cycles 1 and 2 will be summated for each subject. If this total dose is < 23 Gy, the remaining allowable body activity for that subject will be calculated according to the following formula:

$$1000 \times (23 \text{ Gy} - \text{summed renal dose (Gy)}) / \text{renal dose per activity (mGy/MBq)}.$$

All subjects will receive a concomitant amino acid infusion as renal protectant¹³. A parenteral amino acid solution which supplies ≥ 27 g each of lysine and arginine in 2 liters of normal saline (≤ 800 mOsm/L) will be administered IV at a max of 8.3 mL/kg/hour (max 450 mL/hr) for 4 hours to begin 30 minutes prior to infusion of ⁹⁰Y-DOTATOC. Initial infusion rate should be 300mL/hr or less; if tolerated for initial 30 min, rate may be increased to max rate. The total minimum volume which shall be infused is 1600 mL. This will constitute an off-label use of these approved amino acid solutions due to the higher than recommended volume infused. Any further information regarding dosing should be obtained from the manufacturer's instructions.

Patients will be pre-medicated with EMEND and Lorazepam, and/or another anti-emetic, 30 minutes prior to the Amino Acid infusion.

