1.5 Study design

This is a Phase 2 peptide receptor radionuclide therapy trial of ^{90}Y -DOTATOC in patients with somatostatin receptor positive tumors. The somatostatin receptor targeting of the therapeutic will be checked with ^{68}Ga -DOTATOC PET-CT imaging prior to therapy. Treatment consists of 3 cycles, 6-8 weeks apart. Cycle 1 dose is fixed with Cycles 2 and 3 doses to be determined by dosimetry-based calculation of renal doses from previous cycles not to exceed 23 Gy for the total renal dose.

^{68}Ga -DOTATOC PET imaging and ^{90}Y -DOTATOC peptide receptor radionuclide therapy (PRRT) are readily available in Europe, but neither radiopharmaceutical is approved for use in the United States. We are presently conducting a safety and efficacy trial of ^{68}Ga -DOTATOC PET in adults and children under IND# 114,398, that to date has included over 220 subjects with no serious adverse events. We have conducted a single institution Phase I trial of ^{90}Y -DOTATOC therapy in children and young adults under IND# 61,907 with no serious adverse events¹³, and we have participated in a Phase II trial of ^{90}Y -DOTATOC PRRT in adults, also with no dose limiting toxicities²¹.

The total radiation dose to kidneys with PRRT using ^{90}Y -DOTATOC is currently limited to ≤ 23 Gy for both children and adults. Several reports, including dosimetry performed on children in our Phase I trial, have suggested that this dose limit can safely be raised to as high as 35 Gy to kidneys when performing individualized dosimetry measurements to guide therapeutic dosing of ^{90}Y -DOTATOC^{26,29,30}. We have considerable expertise in the development of theoretical models for dosimetry³¹, as well as experience in performing dosimetry in individual patients^{13,32}. These studies demonstrated a wide variation in renal dose, both between patients and between cycles in any given individual. In this Phase II therapeutic trial, we therefore propose to perform dosimetry for each patient during the first and second cycles of therapy. The method for performing the dosimetry will take advantage of a positron decay component of Yttrium-90 that will allow quantification of radiation dose using PET imaging to measure rate of ^{90}Y -DOTATOC into kidneys, coupled with semi-quantitative measurement of bremsstrahlung energy using single photon emission tomography (SPECT) to follow the body clearance of ^{90}Y -DOTATOC over 72 hrs after injection of the therapeutic dose.

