4.0 Objectives

4.1 Primary Objectives

1. Quantify number of CR, PR, MR, SD and progressions in response to dosimetry-guided PRRT utilizing RECIST 1.1 criteria and ⁶⁸Ga-DOTATOC or ⁶⁸Ga-DOTATATE PET to evaluate efficacy of ⁹⁰Y-DOTATOC therapy in children and adults with neuroendocrine and other somatostatin receptor positive tumors.
2. Monitor renal, hematologic, and clinical toxicities associated with dosimetry-guided ⁹⁰Y-DOTATOC PRRT while maximizing total tumor dose and limiting total renal dose of ⁹⁰Y-DOTATOC to ≤ 23 Gy.

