8.0 Duration of Therapy and Stopping Rules

8.1 Stopping Rules for individual subject

In the absence of treatment delays due to adverse events, treatment may continue for 3 cycles or until one of the following criteria applies:

- Cumulative renal radiation dose exceeds 23 Gy.
- Intercurrent illness prevents further administration of treatment.
- Unacceptable adverse event(s) such as irreversible renal or hematopoietic toxicity.
- Initiation of another tumor specific therapy.
- Patient decides to withdraw from the study.
- General or specific changes in the patient's condition render the patient unacceptable for further treatment in the judgment of the investigator.

Other causes of discontinuation from study:

- Termination of study by Sponsor.
- Subject's condition no longer requires study drug.

* Note: Disease progression alone does not mandate discontinuation of ⁹⁰Y treatment.*

Disease progression per RECIST 1.1 criteria during the follow up period will warrant removal from study.

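### The 23 Gy kidney limit in 6.3 counts previous external beam radiation, but the remaining-activity formula and dosing rules subtract only dose from study cycles

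*Combined protocol and SAP*

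**What the plan says.** **The limit.** Section 6.3 explains that, because pediatric subjects are young, "we limited the total dose to kidneys, including any previous external beam radiation to" 23 Gy.

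**The arithmetic.** The next sentence reads "The dose to kidneys measured in Cycles 1 and 2 will be summated for each subject". If that sum is below 23 Gy, remaining activity is 1000 × (23 Gy − summed renal dose) / renal dose per activity. There is no term for earlier radiation.

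**The dosing rules.** Section 6.0 says "Cycles 2 and 3 doses will be determined by dosimetry-based calculation of renal doses from previous cycles". Section 10.1 allows increases as long as the summed dosimetry measurements stay within 23 Gy. Neither mentions prior dose.

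**How the limit is worded elsewhere.** Primary Objective 2 (4.1) speaks of "while maximizing total tumor dose and limiting total renal dose of" ⁹⁰Y-DOTATOC. Section 1.5 says "The total radiation dose to kidneys with PRRT using" ⁹⁰Y-DOTATOC is limited to that figure for both children and adults. The individual stopping rule in 8.1 is "Cumulative renal radiation dose exceeds 23 Gy", with no statement of which sources count.

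**Entry and records.** Exclusion 4 (5.2) bars external beam radiation to both kidneys but accepts scatter under 500 cGy to one kidney, or radiation to less than half of one kidney with no dose bound. The Appendix III form asks for the date of external beam treatment and whether progression followed, the date of craniospinal treatment, and yes/no for exclusion 4.

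**The concern.** The limit and the calculation that should enforce it, a few lines apart, define total kidney dose differently. A physicist who applies the formula exactly does not apply the limit that introduces it. The two agree only when prior kidney dose is zero, and exclusion 4 admits patients for whom it is not.

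The protocol names the kidney as the normal organ at greatest risk (1.4). Limiting renal dose is part of a primary objective, and the 23 Gy limit drives Cycle 2 and 3 activity. An error here goes straight into the activity given, in the group (children) for whom 6.3 chose the stricter limit.

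**Working it through.** **Inputs from the protocol.** Limit 23 Gy (6.3). Adult Cycle 1 is 120 mCi, Cycle 2 at most 150, Cycle 3 no more than Cycle 2, total at most 420 mCi (6.0, 10.1). Child Cycle 1 is 50 mCi/m². Activity falls 25-50% if the projected three-cycle renal dose exceeds 23 Gy and rises 10-20% if it is well below (10.1). Scatter exception: under 5 Gy to one kidney (5.2).

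**Assumptions.** The protocol gives no renal dose per activity (k, mGy/MBq), so the values of k below are illustrative. Prior dose P is set at 5 Gy, the bound of the scatter exception. Child body surface is taken as 1.0 m². 1 mCi = 37 MBq.

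**1. Largest excess under the scatter exception.** If the formula is used up to the limit, study drug gives 23 Gy and the total is 23 + P.
- One kidney: 23 + 5 = 28 Gy (5/23 = 22% over).
- Averaged over two equal kidneys: 23 + 2.5 = 25.5 Gy (2.5/23 = 11% over).

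Because P is strictly under 5 Gy, both are upper bounds. The protocol does not say which measure applies. For the partial-kidney exception there is no dose bound, so the excess cannot be bounded.

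**2. When excess can occur in an adult.** The ceiling is 420 × 37 = 15,540 MBq.
- With 5 Gy prior, excess starts when study drug can pass 18 Gy: 18,000/15,540 = 1.16 mGy/MBq.
- Study drug can reach the full 23 Gy from 23,000/15,540 = 1.48 mGy/MBq.

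Below 1.16 the activity ceiling prevents any excess.

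**3. Effect of the 10.1 steps.** Three adult cycles of 120 mCi are 360 × 37 = 13,320 MBq. The mandatory reduction starts at 23,000/13,320 = 1.73 mGy/MBq.

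| Case (assumed k) | Cycles, mCi | Study drug, Gy | With 5 Gy prior |
|---|---|---|---|
| Adult, k = 1.5, 20% increase | 120+144+144 = 408 | 408 × 37 × 1.5/1000 = 22.6 | 27.6 |
| Adult, k = 1.5, equal split to 23 Gy | 120+147.2+147.2 = 414.4 | 23.0 | 28.0 |
| Adult, k = 2, 25% cut | 120+90+90 = 300 | 300 × 37 × 2/1000 = 22.2 | 27.2 |
| Adult, k = 2, 50% cut | 120+60+60 = 240 | 240 × 37 × 2/1000 = 17.8 | 22.8 |
| Child 1.0 m², k = 4, unchanged | 50+50+50 = 150 | 150 × 37 × 4/1000 = 22.2 | 27.2 |

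At k = 2 the projection is 13,320 × 2/1000 = 26.6 Gy, so the cut applies; at its maximum the excess disappears. In the child example the projection is 22.2 Gy, below 23, so no cut is required.

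**4. The formula at Cycle 3, as written and with P subtracted.**
- Adult, k = 2, after 120 + 90 mCi: summed dose 210 × 37 × 2/1000 = 15.54 Gy. As written: 1000 × (23 − 15.54)/2 = 3,730 MBq (101 mCi, held to 90 by Cycle 2). With P: 1000 × (23 − 5 − 15.54)/2 = 1,230 MBq (33 mCi).
- Adult, k = 2, after 120 + 60 mCi: summed dose 180 × 37 × 2/1000 = 13.32 Gy. With P: 1000 × (23 − 5 − 13.32)/2 = 2,340 MBq (63 mCi), so the planned 60 mCi stands.
- Child, k = 4, after 50 + 50 mCi: summed dose 100 × 37 × 4/1000 = 14.8 Gy. As written: 1000 × (23 − 14.8)/4 = 2,050 MBq (55 mCi, held to 50). With P: 1000 × (23 − 5 − 14.8)/4 = 800 MBq (22 mCi).

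**5. The stopping rule in 8.1, read as counting prior dose.** Before Cycle 3 the totals are 15.54 + 5 = 20.5 Gy (adult, 25% cut) and 14.8 + 5 = 19.8 Gy (child). Neither exceeds 23 Gy, so in these examples the rule does not act before the cycle that takes the total past the limit.

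**The case against.** **The phrase may be carried over.** The sentence is in the past tense and refers to an Aim 1 that this protocol does not define. Objective 2 and 1.5 tie the limit to study treatment, and 6.0 and 10.1 work from study cycles. If that is the intended limit, the formula is right for everyone and one phrase is stray. This is a serious possibility, and it is why deletion must be offered as a fix. It does not remove the conflict: the phrase stands in the current dosing section, and nothing withdraws it for children.

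**A reader might infer that adults are clearly under-protected.** The documents do not support that. The stated reason concerns pediatric subjects, and on the Objective 2 wording the formula is correct for adults.

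**A reader might infer a danger to patients.** Section 6.3 itself says the safe range "is more likely 30-35 Gy when delivered as divided doses of targeted internal radiation", and 10.1 adds GFR-based reductions. The protocol nevertheless kept 23 Gy, so the finding is a breach of its own limit and no more.

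**A reader might infer that prior kidney dose is recorded nowhere, or that the stopping rule usually fails.** Neither is shown. The calendar in 7.0 takes treatment history, and applying the 500 cGy exception implies some dose estimate; what can be said is that the eligibility form has no numeric field and nothing links such an estimate to the formula. How often the stopping rule would act in time depends on a distribution of renal dose per activity that the protocol does not give.

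**Exposure is narrow.** Agreed: exclusion 4 keeps the number of affected patients small. Its mixed wording (both kidneys in the bar, a single kidney in the exceptions) is a separate matter and adds no weight here.

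**Conclusion.** The point holds, firmly for children and as an open question for adults. As written, the formula can let kidney dose pass the limit stated just before it by up to the prior external beam dose. Under the scatter exception that means at most just under 28 Gy in one kidney, or about 25.5 Gy averaged over two equal kidneys.

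Twenty-eight gray is a ceiling, not a typical result. At an assumed 2 mGy/MBq, an adult dosed by the reduction steps in 10.1 would reach 22.8-27.2 Gy with 5 Gy prior, and at the lower end there is no breach. The sizes rest on assumed renal dose per activity, prior dose at the bound of exclusion 4 and, for the child, an assumed body surface. The protocol gives no count of affected patients; they are probably few.

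**What to change.** The investigators should choose one meaning of the limit and make the text agree.

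- **If prior external beam dose counts:** in 6.3 and 10.1, at least for children, compute remaining activity as 1000 × (23 Gy − prior external beam kidney dose − summed renal dose) / renal dose per activity. Say whether prior dose is taken for the more exposed kidney or as an average, and that no further activity is given when the result is zero or less. Add a line to the Appendix III form for prior kidney dose. State whether the rule covers adults, and align 4.1, 6.0 and 8.1 with that choice.
- **If the limit covers ⁹⁰Y-DOTATOC dose only:** delete the external beam phrase from 6.3 and leave the formula as it is.

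The first option costs one formula term, one form line, a sentence on adults and matching wording. Earlier radiotherapy dose records must be retrieved, and a few previously irradiated patients receive less activity: in the examples above, Cycle 3 falls from 90 to 33 mCi (adult, 25% cut) or from 50 to 22 mCi (child), and is unchanged for the adult on the 50% cut. The second option costs one deletion, but gives up the extra protection that 6.3 now states for children.

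### Section 6.3 counts prior external-beam kidney dose toward the 23 Gy limit, but its remaining-activity formula and the Section 10.1 checks count study drug only

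*Combined protocol and SAP*

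**What the plan says.** Section 6.3 states the limit this way: "we limited the total dose to kidneys, including any previous external beam radiation to" 23 Gy or less. The reason given is "because of the young age of pediatric subjects described in Aim 1". The next sentence defines the quantity used for dosing: "The dose to kidneys measured in Cycles 1 and 2 will be summated for each subject". If that total is below 23 Gy, the remaining allowable activity is 1000 times 23 Gy minus "summed renal dose (Gy", divided by the renal dose per activity in mGy/MBq. There is no external-beam term.

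Other places word the limit by study drug or by cycles:

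- Section 1.5: "renal doses from previous cycles not to exceed 23 Gy for the total renal dose". The same section says that the kidney dose from this therapy "is currently limited to ≤ 23 Gy for both children and adults".
- Section 6.0: "dosimetry-based calculation of renal doses from previous cycles; total renal dose ≤ 23Gy".
- Section 4.1, primary objective 2: the limit is on renal dose from the study drug.
- Section 10.1: dose reductions are triggered by the projected renal dose over three cycles, and increases are checked against the sum of dosimetry measurements. No subject may receive more than 420 mCi.
- Section 8.1: a subject stops when cumulative renal radiation dose passes 23 Gy. The source of the dose is not named.

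Section 5.2, exclusion 4, bars external beam to both kidneys. It accepts scatter under 500 cGy to one kidney, or a field covering less than half of one kidney. The second route has no limit in Gy.

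**The concern.** Read literally, the clause in 6.3 and the formula beside it give different allowable activities whenever prior kidney dose E is above zero, and entry criteria allow that. An investigator who follows the formula could breach the limit stated just above it. Two investigators could also apply stopping rule 8.1 differently to the same subject. Renal dose is the quantity that this trial is built to control, so what the 23 Gy covers should not be in doubt.

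The screening forms shown in Appendix III do not help. They ask for dates of prior radiation, progression since, and a yes or no on exclusion 4. They have no field for kidney dose, so a limit that includes E could not be applied from the recorded data.

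**Working it through.** **Can the two texts be reconciled?** Not by treating the summed renal dose as already containing E: the sentence before the formula defines it as the dose measured in Cycles 1 and 2. Neither 10.1 nor 8.1 adds an E term.

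**Inputs.** From the documents: limit 23 Gy; total cap 420 mCi; adult Cycle 1 of 120 mCi; Cycle 2 at most 150 mCi and Cycle 3 no more than Cycle 2; admitted scatter below 5 Gy to one kidney. Assumed: renal dose per activity r, which the documents do not give (range examined 1.0 to 3.0 mGy/MBq); equal kidney masses; external-beam and radionuclide Gy added one for one, as 6.3's wording implies. The number of subjects with E > 0 is not given.

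**When does an excess arise?** The cap is 420 × 37 = 15,540 MBq. Study drug alone reaches 23 Gy at the cap when r = 23,000 / 15,540 = 1.48 mGy/MBq. For an adult dosed to the cap or to 23 Gy, an excess starts at r = 1000 × (23 − E) / 15,540:

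| E (Gy) | Excess starts above r (mGy/MBq) |
|---|---|
| 1 | 1.42 |
| 2.5 | 1.32 |
| 5 | 1.16 |

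So some excess is possible even where the 420 mCi cap governs. At r = 1.2 and E = 5, study drug gives 15,540 × 1.2 / 1000 = 18.65 Gy, and the total is 23.65 Gy. From r = 1.48 upward the full E is in excess.

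**How large is it for scatter cases?** With E just under 5 Gy to one kidney and study drug at 23 Gy:

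- irradiated kidney: below 23 + 5 = 28 Gy;
- mean of both kidneys: below 23 + 5/2 = 25.5 Gy (25.5 / 23 = 1.109, or 11% over).

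For fields covering less than half of one kidney no ceiling is stated, so no bound follows.

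**Does the reduction rule in 10.1 remove it?** Read as a projection of three 120 mCi cycles, r = 2.0 gives 360 × 37 × 2.0 / 1000 = 26.64 Gy, which triggers a cut of 25-50%.

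| Cut | Total (mCi) | Study drug (Gy) | Irradiated kidney, E = 5 | Two-kidney mean |
|---|---|---|---|---|
| 25% | 120 + 90 + 90 = 300 | 22.20 | 27.20 | 24.70 |
| 50% | 120 + 60 + 60 = 240 | 17.76 | 22.76 | 20.26 |

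A 50% cut removes the excess; a 25% cut does not.

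**Would changing the formula alone suffice?** Take an adult with r = 2.0 and E = 5. The 10.1 target is 23,000 / 2.0 / 37 = 310.8 mCi, so Cycle 2 is (310.8 − 120) / 2 = 95.4 mCi. Cycles 1 and 2 give 215.4 × 37 × 2.0 / 1000 = 15.94 Gy. The printed formula then leaves 1000 × 7.06 / 2.0 = 3,530 MBq (95.4 mCi) for Cycle 3. With E subtracted it leaves 1,030 MBq (27.8 mCi). The whole correction would fall on Cycle 3, so the 10.1 target has to change too.

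**The case against.** The strongest reply is that the external-beam clause is a leftover. It is in the past tense, while the summation and the formula are in the future tense. It gives a pediatric reason, although Section 1.5 applies 23 Gy to children and adults alike. It refers to an Aim 1 that this protocol does not have, and the same paragraph cites reference 58 when the list in Section 15.0 ends at 38. Sections 1.5, 4.1, 6.0 and 10.1 all speak of study drug, cycles or dosimetry. In the treatment table, the Cumulative Renal Radiation column stands next to the cumulative study-drug column, with its 23 Gy entry at Cycle 3. Exclusion 4 also keeps prior kidney exposure limited.

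Most of this stands, and it favors a study-drug limit. A reader might infer from 6.3 that the plan clearly means to count external beam and that the formula is the mistake; the documents do not support going that far. But the reply does not remove the conflict. The clause is current text, leads directly into the formula, and is nowhere withdrawn. If it is a leftover, it should be deleted.

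A reader might also infer that the formula exposes subjects to expected renal harm. The documents do not support that either: 6.3 itself says that the safe range "is more likely 30-35 Gy when delivered as divided doses of targeted internal radiation".

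**Conclusion.** The point holds as an inconsistency in a stated safety limit. For subjects with prior kidney dose, the printed dosing rule can exceed the limit in 6.3 by up to E. The textual conflict needs no assumption. The sizes do: they rest on an assumed renal dose per activity, equal kidney masses and one-for-one addition of Gy.

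The 28 and 25.5 Gy figures must not be read as bounds for every admitted subject. They cover scatter cases only, because the partial-kidney route has no dose ceiling. The affected group is probably small, but its size cannot be taken from the documents. Which of the two texts is wrong is for the sponsor to say. The weight of the other sections is on the study-drug reading.

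**What to change.** The sponsor should state which limit is meant and make the text agree.

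**If prior external beam counts** (for all subjects, or for children only, whichever is intended): use 1000 × (23 − E − summed renal dose) / renal dose per activity in 6.3; use 23 − E for the target and checks in 10.1; define E (irradiated kidney or mean of both, and how partial fields are handled); record E in Gy beside exclusion 4 on the screening form; and align 4.1 and 8.1.

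**If it does not count:** delete the clause from 6.3 and say in 8.1 that cumulative means study-drug dose. This costs only wording, but gives up the allowance for prior radiation that 6.3 now states.

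The first option costs Cycle 2 and 3 activity in affected subjects, against the aim of maximizing tumor dose. For an adult with E = 5 Gy at an assumed 2.0 mGy/MBq, the allowance with E counted is 18,000 / 2.0 / 37 − 120 = 123.2 mCi:

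| Rule in 10.1 that sets Cycles 2+3 | As printed (mCi) | With E (mCi) | Loss |
|---|---|---|---|
| Target split | 190.8 | 123.2 | 35% |
| 25% reduction | 180 | 123.2 | 32% |
| 50% reduction | 120 | 120 | none |

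If E is defined as the two-kidney mean (2.5 Gy), the target-split loss is 190.8 to 157.0 mCi, or 18%.

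For a child of 1.0 m² (assumed; Cycle 1 of 50 mCi) held to the 10-20% increase rule, Cycles 2 and 3 total at most 60 + 60 = 120 mCi. At 2.0 mGy/MBq the kidney total is 170 × 37 × 2.0 / 1000 + 5 = 17.6 Gy, so nothing is lost. At 3.0 the allowance is 18,000 / 3.0 / 37 − 50 = 112.2 mCi, a loss of about 6.5%.

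Prior kidney dose must also be retrieved from radiotherapy records. Checking the 500 cGy criterion already calls for an estimate in scatter cases; for subjects admitted under the partial-kidney route it is extra work.
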